Sacrospinous ligament fixation is a common method of repairing apical support for pelvic organ prolapse but it currently suffers from a high rate of postoperative buttock and posterior thigh pain. Rates of buttock and thigh pain 6 weeks after sacrospinous ligament fixation with the widely used Capio[™] Slim device (Boston Scientific) are about 15-16% with immediate postoperative pain occurring in 55-84% of patients. Our study is a randomized controlled single-blind study with the primary goal of investigating if there is an improvement in the rate of buttock and posterior thigh pain 1 day, 1 week, and 6 weeks after sacrospinous ligament fixation with a new device, the Anchorsure® Suture Anchoring System (Neomedic) compared to the widely utilized Capio[™] Slim (Boston Scientific) device. We will enroll 60 patients who are planned to undergo sacrospinous ligament fixation for treatment of pelvic organ prolapse. The patients will be randomized into two study groups; one will have sacrospinous ligament fixation using the Capio[™] Slim device and the other with the Anchorsure[®] device. The patient's pain will be recorded via numerical rating scales (NRS), a validated pain evaluation tool. The study is powered to detect a 2.5 point difference in pain between the two groups, a value that has been shown in studies to be clinically significant to patients. Secondary outcomes of surgeon satisfaction and efficiency with the devices will be assessed via surgeon guestionnaires. The demonstration of a significant decrease in postoperative buttock or thigh pain. improved surgeon efficiency, or decreased operative time with the use of the Anchorsure device will demonstrate an advantage of the suture anchoring devices over suture capture devices and will fuel the need for a larger efficacy study for the Anchorsure device. Demonstration of improved safety and/or improved surgical outcomes could ultimately change the standard in sacrospinous ligament fixation surgical technique.

BACKGROUND AND SIGNIFICANCE

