Pelvic organ prolapse (POP) describes the loss of anatomic support of the vagina where women present with a vaginal bulge with or without associated bladder, bowel or sexual complaints. The lifetime risk of undergoing surgery for female pelvic organ prolapse is estimated at 19%.¹ One of the most common approaches to repair of apical vaginal prolapse is suspension of the vaginal apex or cervix to the **sacrospinous ligament** using suture material, a technique that avoids entry into the peritoneal cavity.

[figure not shown]
The current standard practice is to use a self-capturing suture delivery systems like the **Capio**^M **Slim Suture Capturing Device.** This procedure is associated with a significant risk of **postoperative buttock and posterior thigh pain.**^{2,3} Such pain can arise from entrapment of the pudendal or sciatic nerves given their close anatomic proximity to the sacrospinous ligament suture fixation (Figure 1) or from entrapment of the levator ani nerve that runs along the surface of the

coccygeus muscle.⁴ Immediate postoperative buttock and posterior thigh pain with the Capio[™] device has been reported in 55-84% of patients with persistent pain at 6 weeks postoperatively in 15-16%.^{4,2}

The use of an anchor-based system into the sacrospinous ligament, as opposed to a suture-based system, could theoretically reduce the risks of suture entrapment particularly of the levator ani nerve thereby reducing the high rate of postoperative buttock and thigh pain. Anchor-based pelvic organ prolapse repair systems have been studied and utilized domestically and internationally for mesh-based prolapse repair kits. However, there is currently little evidence about the rates of postoperative buttock and posterior thigh pain from anchorbased fixation to the sacrospinous ligament for native tissue vaginal repair.

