The **Anchorsure**® (Figure 2 and Figure 3) is a new FDA-approved sacrospinous ligament fixation device that deploys a permanent anchor directly into the ligament and requires high pull-out force for extraction. The device is a Class II surgical device that was FDA approved via a 510(k) premarket notification in 2012. Its approval was based on the FDA approved device Surelift® (Neomedic). Surelift® uses the same anchoring system as Anchorsure but is attached to vaginal mesh as opposed to Anchorsure which is designed to attach to suture material. Surelift® is used widely and has been studied in abstracts⁵⁻⁹ and a published study¹⁰ confirming safety and surgical efficacy. Abstracts on the use of Anchorsure have additionally been published indicating safety and efficacy of use.^{11,12} A summary of the available data for the Capio Slim[™], Surelift®, and Anchorsure® devices is listed in Appendix 1.

The **primary aim** of this study is to conduct a prospective randomized trial of this new anchor-based system versus our current suture-capture-based fixation systems to compare the rates of postoperative buttock and posterior thigh pain. This is important because decreased buttock and posterior thigh pain can reduce patient suffering and potentially reduce postop narcotic use. Our **secondary aims** are to compare intraoperative complications, general postoperative pelvic pain and post-hospitalization opioid use as well as surgeon satisfaction and surgical efficiency with the device. The demonstration of a significant decrease in postoperative buttock or thigh pain, improved surgeon efficiency, or decreased operative time with the use of the Anchorsure device will demonstrate an advantage of the suture anchoring devices over suture capture devices and will fuel the need for a larger efficacy study for the Anchorsure device. Demonstration of improved safety and/or improved surgical outcomes could ultimately change the standard in sacrospinous ligament fixation surgical technique.

[figure not shown]
[figure not shown]

Figure 2. Anchorsure® System¹³

[figure not shown]

Figure 3. Anchorsure® System application to sacrospinous ligament¹³

STUDY OBJECTIVES

Hypothesis 1: Anchorsure® System will reduce postoperative buttock and posterior thigh pain at 1 day, 1 week, and 6 weeks following sacrospinous ligament fixation compared to the Capio[™] Slim Suture Capturing Device

Specific Aim 1:

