To conduct a prospective, randomized, single-blind trial of sacrospinous ligament fixation of the cervix or vaginal apex using Anchorsure® system versus the CapioTM Slim device in women with \geq Stage II pelvic organ prolapse who are undergoing native tissue vaginal repair. The **primary outcome** will be the level of postoperative pain using a 10-point numerical rating scale (NRS) on postoperative day 1, week 1, and 6 weeks postoperatively for pain that is localized to the posterior thigh or buttocks on the side(s) that the sacrospinous fixation was performed. The difference in mean pain ratings will be at least 2.5 on the 10-point NRS.

Hypothesis 2: Surgeon satisfaction, surgical efficiency, intraoperative complications, objective surgical success, symptomatic success, opioid use within the first week postoperatively following hospitalization, and overall postoperative pelvic pain will be similar for both devices.

Specific Aim 2:

The **secondary outcomes** will compare overall surgeon satisfaction with the 2 devices using a 5-point Likert rating scale and surgical efficiency measured in minutes from the start of the use of the surgical device until the surgeon is satisfied with the application of all sacrospinous sutures (does not require the sutures to be tied down). Intraoperative complication related to sacrospinous ligament suspension will be recorded including the need for suture or anchor replacement, hemorrhage that requires additional surgical interventions or blood transfusion, and equipment malfunction. General postoperative pelvic pain will be assessed at postoperative day 1, week 1, and 6 weeks along with buttock and posterior thigh pain via NRS questionnaires. Objective apical repair anatomical success will be assessed at the 6 week postoperative visit via a POP-Q examination with Stage II or greater indicating anatomical failure. Symptomatic surgical success will be evaluated by statistically significant increases or decreases in the responses to the PFDI-20 and PFIQ-7 questionnaires at the 6 week postoperative values.

SUBJECT SELECTION

Inclusion Criteria

- 1. Female patients
- 2. At least 21 years of age
- 3. Surgical plan that includes a native tissue vaginal repair with apical support via sacrospinous ligament fixation. We will permit both hysteropexy and post-hysterectomy sacrospinous ligament suspension
- 4. Understanding and acceptance of the need to return for the 6 week followup visit

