This study is a head to head two sample comparative study. The null hypothesis is that there is no difference in the prevalence of immediate postoperative new buttock or posterior thigh pain with the use of the Anchorsure® System compared to the Capio[™] Slim device for sacrospinous ligament fixation. In prior published study by Ferrando et al the mean postoperative day 1 buttock or posterior thigh pain had a greater standard deviation (2.7-2.9) compared to week

1 and week 6 data. Therefore for our power calculation used an expected standard deviation of 2.9 to provide confidence in our power of assessing the difference in pain scores across all three timepoints.²² A decrease in in-hospital postoperative buttock or posterior thigh pain prevalence of 2.5 on a 10-point scale was chosen as clinically significant and is consistent with published data.^{22,18,17} Using a standard deviation of 2.9 and a difference in pain scores of 2.5 setting the level of significance, 21 patients are required in each group to provide a power of at least 80% to reject the null hypothesis (H0) that the Anchorsure® System does not lead to significantly less postoperative buttock and posterior thigh pain than does the Capio[™] Slim Device in favor of the alternate hypothesis that the Anchorsure® System leads to significantly less postoperative pain than the Capio[™] Slim Device using a two-sample normal approximation test of means with a two-sided 5% significance level. Assuming a 15% loss to follow-up or drop-out rate for the duration of the study, the total enrollment goal is 48 patients (24 in each group). The null hypothesis will be declared rejected if the mean of immediate postoperative buttock and posterior thigh pain with use of the Anchorsure® device is less from the mean with the use of the Capio[™] Slim device with a p-value of 0.05 or less. The power calculations and their adjustment from the original study goal of 60 recruited patients (using 90% power and a standard deviation of 3) were confirmed with the Wake Forest Baptist Hospital CTSI Biostatistics Department.

Form / Intervention	Preop Clinic	Intra- operatively	Day 1	Week 1	Week 6
Informed Consent	Х				
Study Inclusion Form	Х				
Preop Baseline Data Form with					
Charlson Comorbidity Index and	Х				
POP-Q					
PFDI-20 and PFIQ-7 Forms	Х				Х
NRS Pain Questionnaires	Х		Х	Х	Х
Oral Opioid Use Questionnaire				Х	
Randomization		Х			
Adverse events		Х	Х	Х	Х
Surgeon Questionnaire		Х			

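### The power statement carries one 2.5-point difference to week 6, where the plan's own six-week pain rates make a reduction of that size implausible

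*Combined protocol and SAP*

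**What the plan says.** Hypothesis 1 (Study Objectives) is that Anchorsure "will reduce postoperative buttock and posterior thigh pain at 1 day, 1 week, and 6 weeks". Specific Aim 1 makes the NRS level at those three visits the primary outcome and attaches one figure to all of them: "The difference in mean pain ratings will be at least 2.5 on the 10-point NRS". The summary at the start of the protocol says "The study is powered to detect a 2.5 point difference in pain between the two groups" and names no visit. Clinical Outcomes also defines 2.5 points as clinically significant without limiting it to a visit.

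The Power Calculation notes that day-1 pain in the cited earlier trial "had a greater standard deviation (2.7-2.9) compared to week" 1 and week 6. It therefore adopts 2.9, "to provide confidence in our power of assessing the difference in pain scores across all three timepoints". No separate difference is given for week 6.

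The same paragraph also points to one early visit: "A decrease in in-hospital postoperative buttock or posterior thigh pain prevalence of 2.5 on a 10-point scale was chosen as clinically significant". Its null hypothesis and rejection rule are likewise worded for immediate postoperative pain.

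On how common pain is with Capio, the summary says the six-week rates "are about 15-16% with immediate postoperative pain occurring in 55-84% of patients". Background and Significance repeats the 15-16%. Appendix 1 gives 63.2% at week 1 and 15.3-26.9% at weeks 4-6.

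**The concern.** Power depends on the SD and on the difference assumed. The plan argues only from the SD: because 2.9 is the largest of the three visits' values, power is taken to be safe at all three. That holds for a true 2.5-point difference at each visit. It gives no assurance at a visit where few patients have pain, because the comparator mean is then close to the floor of the scale and leaves little room for a reduction.

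Week 6 is a primary time point, and persistent pain is part of the case for the trial. As written, a reader would take the 80% power to cover week 6, and could read a non-significant week-6 t-test as showing no benefit on persistent pain.

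**Working it through.** **1. The plan's own figure.** Inputs from the Power Calculation: difference 2.5, SD 2.9, two-sided 5%, 80% power, normal approximation.

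n per group = 2 × (1.96 + 0.8416)² × 2.9² / 2.5² = 21.1, against 21 stated. With 21 per group the standard error is 2.9 × √(2/21) = 0.895, and power for a true 2.5 points is Φ(2.5/0.895 − 1.96) = 79.8%. The figure reproduces to rounding. With a smaller SD the power for 2.5 points is higher, for example 98.2% at an assumed SD of 2.0.

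**2. The largest reduction possible at each visit.** Assumption, not in the documents: patients not counted as having pain score 0 on a 0-10 scale. Then the Capio mean = pain rate × mean score among sufferers. The largest reduction is rate × 10, with every sufferer at 10 and every Anchorsure patient at 0. For the Capio mean even to equal 2.5, sufferers must average 2.5 / rate.

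| Visit | Capio pain rate (source) | Largest reduction | Sufferer mean needed |
|---|---|---|---|
| Day 1 | 55-84% (summary) | 5.5-8.4 | 4.5-3.0 |
| Week 1 | 63.2% (Appendix 1) | 6.3 | 4.0 |
| Week 6 | 15-16% (summary, Background) | 1.5-1.6 | 16.7-15.6, off the scale |
| Weeks 4-6, upper value | 26.9% (Appendix 1) | 2.69 | 9.3 |

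The rate must be at least 2.5/10 = 25% before 2.5 points is possible at all under this assumption. If the 10-point scale runs from 1 to 10, the limits fall to rate × 9: 1.35-1.44 at 15-16% and 2.42 at 26.9%.

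**3. Relaxing the zero-score assumption.** For a Capio mean of 2.5, the patients not counted as having pain would have to average:
- with every sufferer at 10: (2.5 − 1.6)/0.84 = 1.07 at 16%, and (2.5 − 1.5)/0.85 = 1.18 at 15%;
- with sufferers averaging 4: (2.5 − 0.64)/0.84 = 2.21 at 16%, and (2.5 − 0.60)/0.85 = 2.24 at 15%.

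Even then, a 2.5-point reduction requires an Anchorsure mean of 0.

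**4. Whether the smaller week-6 SD makes up for it.** The documents give no week-6 scores, so this is an illustration only. Assume that sufferers' scores average 3 to 6 (SD 2, clipped to 1-10), that others score 0, 21 per group, and a pooled t-test at two-sided 5%. Simulation with 40,000 trials per scenario gives:

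| Scenario | Rate | Difference (points) | Power |
|---|---|---|---|
| Pain rate halved | 15-16% | 0.2-0.5 | about 7-11% |
| Pain rate halved | 26.9% | 0.4-0.8 | about 15-17% |
| Pain eliminated | 15-16% | 0.5-1.0 | about 23-40% |
| Pain eliminated | 26.9% | 0.9-1.6 | about 71-82% |

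The pooled SD in these scenarios is 0.9-2.5, already below 2.9. A smaller SD therefore restores power close to 80% only when pain is eliminated completely at the upper rate.

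**The case against.** Four points can be made for the plan.

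- **The limit rests on an assumption.** The documents quote prevalences and do not say how the cited studies defined pain. If only notable complaints were counted, the remaining patients may score above 0 and the 1.5-1.6 limit rises. This stands, and it is why the point is one of plausibility rather than proof. However, the exclusion of significant buttock or leg pain in the past 3 months makes scores near 0 reasonable for patients without new pain, and step 3 shows how far the assumption would have to fail.
- **Appendix 1 leaves room.** A reader might infer that 2.5 points is impossible at week 6. The documents do not support that: at 26.9% the limit on a 0-10 scale is 2.69. The scores needed are extreme, but they exist.
- **The sentence is correct as a conditional, and a clinically important difference is not a forecast.** This also stands. A reader might infer that the trial is too small for its stated target; it is not, since power for a true 2.5 points is about 80% at SD 2.9 and higher at a smaller SD. But Specific Aim 1 words the 2.5 points as what the difference will be, and the Power Calculation offers assurance at all three visits without asking whether that difference can be expected at each.
- **The decision rule concerns immediate pain, so week 6 lies outside it.** This is a partial answer. The same paragraph extends power to all three visits, and Hypothesis 1, Specific Aim 1 and Clinical Outcomes all make week 6 primary. The two descriptions conflict and need to be reconciled.

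**Conclusion.** The concern holds in a limited form. The assurance of power at week 6 does not follow from a conservative SD, because a 2.5-point reduction there is implausible on the plan's own pain rates: at most 1.5-1.6 points at 15-16%, and 2.69 at 26.9% only in near-extreme circumstances. This depends on patients not counted as having pain scoring about 0, and it concerns a reduction with Anchorsure, which is the stated hypothesis. The 26.9% covers weeks 4-6 rather than week 6 alone.

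The sample size stands, and the limit does not bear on day 1 or week 1. The week-6 power figures in step 4 rest on assumed score distributions and range from about 7% to 82%. They show why the smaller SD is no general remedy; they are not estimates for this trial. The fault is an over-broad power statement that conflicts with other sentences in its own paragraph. It should be corrected, but it is not a defect of the design.

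**What to change.** In the Power Calculation:

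- Remove week 6 from the statement of 80% power for 2.5 points.
- Reconcile the reference to all three visits with the sentences on in-hospital and immediate postoperative pain, so that the paragraph names the same visit or visits throughout. Week 1 needs an explicit decision: the limit above does not rule it out, but those sentences do not describe it.
- Add wording such as: *The trial is not powered at week 6 for the smaller differences expected from the reported six-week pain rates. The week-6 mean difference will be reported with a 95% confidence interval, and a non-significant week-6 result will not be interpreted as evidence of no benefit.*

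Align the 2.5-point sentences in the summary and in Specific Aim 1. The power figures assumed in this review should not go into the protocol. If the sponsor wants to quantify week-6 power, the week-6 means and SDs in the cited trial that supplied the SD are the place to start, and they would also test the zero-score assumption.

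The cost is wording in three places, through an amendment with IRB approval as Study Monitoring requires, and giving up the stated week-6 power claim. Sample size, visits, primary outcome and t-test do not change.

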Access to the retroperitoneal space will be accomplished either via a circumferential pericervical, an anterior, or a posterior. The method of surgical approach will be recorded. Sharp and blunt dissection will be performed to gain access to the sacrospinous ligament(s). Surgeon discretion will determine if unilateral or bilateral fixation is performed for vaginal vault suspension but only unilateral sacrospinous ligament suspension will be permitted for hysteropexy. Surgeon discretion will determine the type and number of sutures or anchors to be placed through the sacrospinous ligament and this data will be recorded. All sutures and anchors placed into the sacrospinous ligament will be placed at least 2cm medial to the ischial spine. Suture(s) will be placed through any anchors with the choice of suture to be determined by the surgeon as this is not anticipated to interfere with any results. The suture(s) placed through anchors or the sacrospinous ligament directly will then be attached to the cervix and/or vaginal apex. Sacrospinous sutures will be tied down once all mid-vaginal repairs are completed. Transvaginal hysterectomy, bilateral salpingectomy, bilateral oophorectomy, and enterocele repair procedures will be performed prior to sacrospinous ligament fixation.

POST-INTERVENTION ASSESSMENTS

The primary study endpoints will be assessed on postoperative day 1, postoperative week 1, and postoperative week 6 via a NRS. Day 1 questionnaires will be given during morning rounds. 1 week following their procedure, patient's will be called at home to remind them to fill out the week 1 questionnaire that would have been given to them during their hospital stay. This questionnaire will be accompanied with a pre-paid and pre-addressed envelope for the patient to use or, if desired, they can bring the completed week 1 questionnaire to their week 6 follow up appointment. All patients will return to the clinic for 1-week and 6-week post-surgery follow up appointments and will fill out an NRS pain assessment (1-week and 6-week), opioid use questionnaire (1-week), PFDI questionnaire (6-week), physical examination including POP-Q (6-week), and review of any postoperative complications (1-week,6-week).

Clinical outcomes

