This trial has a **primary** outcome of level of postoperative buttock or posterior thigh pain on postoperative day 1, week1, and 6 weeks as measured using the NRS. An independent t-test will be used to compare the means of the NRS scores from the two groups. The NRS is one of the most common validated pain questionnaire modalities.^{17,18,19,20,21} A clinically significant difference will be considered 2.5 on the 10-point NRS based on a prior paper assessing buttock pain from sacrospinous ligament fixation²² and with published studies assessing clinically meaningful decreases in acute pain.^{18,17} The patient's will be given copies of the NRS questionnaire which will be collected in person on postoperative day 1, week 1, and 6 weeks postoperatively.

Secondary outcome measures will assess the degree to which the study intervention influences surgeon satisfaction, surgical efficiency, adverse events intra- and postoperatively, surgical success, symptomatic success, and the level of postoperative general pelvic pain. Surgeon satisfaction will be assessed via a 5-point rating scale (very dissatisfied, somewhat dissatisfied, neutral, satisfied, very satisfied) and treated as categorical values. Surgical efficiency will be assessed as continuous data measured as a means in minutes. Adverse events will be evaluated as dichotomous data. All adverse events will be reported by the Dindo classification system. Short-term objective surgical success will be assessed by a postoperative exam at 6 weeks and descent of the vaginal apex beyond TVL/2 will be considered surgical failure. Symptomatic success will be assessed by the PDFI-20 guestionnaires to be given at 6-weeks post-operation and compared to preoperative values. The patient's will also be queried about their general pelvic pain on the same questionnaires used to assess buttock and posterior thigh pain. Oral opioid use following hospitalization until postoperation day 6 will be recorded via opioid use questions on the 1 week postoperation guestionnaire. The opioid dose will be converted into morphine equivalents for data analysis. Statistical analysis will be done in collaboration with the Wake Forest Baptist Hospital CTSI Biostatistics Department. Independent t-tests will be used for all continuous data, except for the PFDI and PFIQ data that will use paired t-tests as the two samples are dependent. Chi-square tests will be used for all dichotomous and categorical data.

POWER CALCULATION:

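### After the assumed 15% loss, 24 per group leaves 20.4, below the 21 required, so the stated 80% power is narrowly missed at SD 2.9

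*Combined protocol and SAP*

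**What the plan says.** The Power Calculation section states that "21 patients are required in each group to provide a power of at least 80% to reject the null hypothesis", for a difference of 2.5 NRS points and an SD of 2.9, "using a two-sample normal approximation test of means with a two-sided 5% significance level". The SD is the upper end of a day 1 range of 2.7 to 2.9 from a prior trial. The section says SDs at weeks 1 and 6 were smaller, without giving values, and describes its choice as an "expected standard deviation of 2.9 to provide confidence in our power of assessing the difference in pain scores across all three timepoints".

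Enrolment follows in the next sentence: "Assuming a 15% loss to follow-up or drop-out rate for the duration of the study, the total enrollment goal is 48 patients", stated as 24 in each group. The decision rule reads "The null hypothesis will be declared rejected if the mean of immediate postoperative buttock and posterior thigh pain" is lower with Anchorsure at p of 0.05 or less.

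The planned analysis, under Clinical outcomes, is a t-test: "An independent t-test will be used to compare the means of the NRS scores from the two groups".

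The opening summary still gives an enrolment of 60. The Power Calculation section treats 60 as superseded: "The power calculations and their adjustment from the original study goal of 60 recruited patients".

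**The concern.** Two adjacent sentences do not fit together. One sets a minimum number of evaluable patients. The next applies a loss rate and sets an enrolment that, at that rate, leaves fewer than the minimum. Two smaller choices push the same way: 21 is the formula's result rounded down, and the calculation uses a normal approximation although the analysis is a t-test.

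At stake is whether the power claimed for the primary comparison is the power the design delivers. A reader relying on the protocol would take 80% as a floor after attrition, and would find two different enrolment targets in the same document.

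**Working it through.** **Inputs.** Difference 2.5, SD 2.9, two-sided alpha 0.05, target power 80%, 21 per group required, 15% loss, 24 per group enrolled (all from Power Calculation). Independent t-test (Clinical outcomes).

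**1. The plan's own number.** By the normal approximation,

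n per group = 2 × (1.960 + 0.842)² × 2.9² / 2.5² = 21.12.

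The plan's 21 is this value rounded down. Rounding up gives 22.

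**2. The attrition step.**
- Adding 15%: 21 × 1.15 = 24.15, which rounds down to 24. This matches the plan.
- Dividing by the retained share: 21 / 0.85 = 24.7, so 25 per group, 50 in total.
- Retained from the planned enrolment: 24 × 0.85 = 20.4 per group (48 × 0.85 = 40.8 in total, against 42 required).
- Loss that 24 per group can absorb while keeping 21: 1 − 21/24 = 12.5%.

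**3. Power at the numbers retained.** The standardised difference is 2.5 / (2.9 × √(1/n₁ + 1/n₂)). Normal power is Φ(that value − 1.960). The t-test power uses the noncentral t distribution with n₁ + n₂ − 2 degrees of freedom. For 20.4 per group, the standardised difference is 2.753 and Φ(0.793) = 0.786.

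| Evaluable per group | Lost of 48 | Normal | t-test |
|---|---|---|---|
| 24, 24 | 0 | 84.8% | 83.2% |
| 22, 23 | 3 | 82.4% | 80.7% |
| 22, 22 | 4 | 81.6% | 79.8% |
| 21, 22 | 5 | 80.7% | 78.8% |
| 21, 21 | 6 | 79.8% | 77.8% |
| 20, 21 | 7 | 78.8% | 76.8% |
| 20.4, 20.4 | 7.2 | 78.6% | 76.6% |
| 20, 20 | 8 | 77.8% | 75.7% |

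Fifteen percent of 48 is 7.2. With losses split evenly, 80% holds for up to 5 lost (normal) or 3 lost (t-test).

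**4. Difference detectable with 80% power after the full loss (SD 2.9, 20 to 20.4 per group).** 2.54–2.57 points (normal) or 2.61–2.64 points (t-test), against the 2.5 the plan calls clinically significant.

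**5. SD at which the claim would hold after the full loss.** For 2.5 points and 80% power with 20 to 20.4 per group, the SD must be no more than about 2.82–2.85 (normal) or 2.75–2.78 (t-test). At SD 2.7, 20 per group gives 83% (normal) or 81% (t-test).

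**The case against.** The strongest reply is that an SD of 2.9 together with the full 15% loss may describe no actual visit. The SD is the top of a day 1 range, whereas the loss runs to week 6. The decision rule concerns immediate postoperative pain. Randomisation takes place in the operating room, and "Day 1 questionnaires will be given during morning rounds", so little loss before day 1 is plausible, though the plan does not say so. With none, day 1 power is 84.8% (normal) or 83.2% (t-test), above target. At the later visits the SD is said to be smaller, and a modest reduction restores 80%. Because those SDs are not given, a shortfall at weeks 1 and 6 is not demonstrated.

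It can also be said that the gap is about one patient (40.8 retained against 42), that 79.8% at 21 per group rounds to 80%, and that about two of the missing points come from changing formula rather than from the attrition step.

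All of this limits the weight of the point, and the size should be reported accordingly. It does not remove the inconsistency. The section itself applies whole-study loss to a calculation at SD 2.9 and says that SD is meant to cover all three timepoints. On those terms the enrolment does not keep the number the section says is required.

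**Conclusion.** The concern holds. On the plan's own inputs, 24 per group does not retain 21 after 15% loss, and power is 1 to 4 points below the stated minimum: 77.8–78.6% by the stated approximation and 75.7–76.6% by the planned test. Part of the gap precedes attrition: 21 per group already gives 79.8% (normal) or 77.8% (t-test).

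These figures rest on SD 2.9, a true difference of 2.5, the full 15% loss, and losses split evenly between groups. They are conservative for day 1 if few patients are lost by then, and for later visits if the SD is below the thresholds in step 5. The shortfall would not by itself alter the reading of a null result. Separately, the enrolment of 60 in the opening summary is out of date. This should be fixed because the stated power is incorrect and correcting it costs almost nothing.

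**What to change.** Keep 48 and revise the text of the Power Calculation section:

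- Replace the minimum-80% claim with the power at the number expected to be retained, naming the test: about 76–77% by t-test (78–79% by the normal approximation) at SD 2.9 and 2.5 points after 15% loss. Label this as the conservative case, since it pairs a day 1 SD with whole-study loss.
- Give day 1 power separately: about 83% by t-test, on the stated assumption that no one is lost by then.
- State the difference detectable with 80% power after loss: about 2.6 points by t-test.
- Change 60 to 48 in the opening summary.

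This needs no extra patients and no change to the analysis. The only cost is a slightly less favourable power statement.
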